11.1. DAWN eligible vs DAWN ineligible

The primary efficacy and safety analyses (mRS shift at 90 days, mRS 0-2 at 90 days, death rate and SICH rate) will be performed in “DAWN eligible” vs. “DAWN-ineligible” subgroups. The DAWN-ineligible subgroup will be defined as any patient who has one or more of the following characteristics:

- Pre-stroke mRS >1
- Baseline NIHSS <10
- Baseline ischemic core > 51 ml (based on Central Lab reading)
- Age >80 with baseline ischemic core > 21ml (based on Central Lab reading)
- Age < 80 and NIHSS < 20 and Baseline ischemic core >31 ml (based on Central Lab reading)

All other patients will be considered “DAWN eligible”.

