Endovascular Therapy Following Imaging
Evaluation for Ischemic Stroke 3

Statistical Analysis Plan

NCT02586415

September 8, 2017

[name], Principal Investigator
Stanford University
Stanford, California 94305

Memorandum

Date: July 19, 2017

To: The DEFUSE 3 SAP

From: [REDACTED]

RE: Interim Analysis Plan, as requested by the DEFUSE 3 DSMB

An early interim analysis was requested by NINDS, in response to external information generated from the DAWN trial, in order to make a determination as to whether DEFUSE 3 should continue in the original population or a subpopulation, or be terminated early.

The details of this proposed analysis were put forth in Version 2.0 of the DEFUSE 3 SAP. On June 23, via email communication from [REDACTED], a revision to that analysis plan was requested. The details of the plan, as requested by the DSMB, are outlined below; we have noted details which deviate from the plan outlined in the SAP. This information is documented in a memo to the SAP, rather than a revision to the SAP, in order to keep the study team blinded.

For this early interim analysis, the overall null hypothesis for the primary endpoint will be tested using the Wilcoxon rank sum statistic and asymptotic pvalue, generated via the PROC NPAR1WAY procedure in SAS. The 90-day mRS for subjects who have not yet reached the end of the study protocol will be imputed with their respective 30-day mRS. Subjects with no 30-day or 90-day mRS scores will be excluded. This is as specified in Version 2.0 of the DEFUSE 3 SAP. The SAP stipulates a one-sided level of significance of 0.023 for this analysis; however, the DSMB will meet to decide on decision rules prior to reviewing the results, and their decision rules are presumed to override the level of significance stated in the SAP.

The DSMB requested that the above analysis be repeated in the subgroup of DEFUSE 3 subjects who are considered DAWN-eligible. The DSMB will decide whether to review the subgroup analysis at the time of the meeting.

Per DSMB request, the power of these analyses at the available sample size will be calculated, as will the nominal threshold for declaring efficacy or harm if this was a typical unplanned interim analysis.

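### SAP 11.1 assigns age 80 to neither age-specific core limit, so some 80-year-olds are DAWN-eligible by default at core volumes that exclude patients aged 79 and 81

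*SAP*

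**What the plan says.** SAP 11.1 repeats the main efficacy and safety analyses (mRS shift, mRS 0-2, death, sICH) in DAWN-eligible and DAWN-ineligible patients. A patient is ineligible if any one of five criteria is met. Three apply at every age:

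- "Pre-stroke mRS >1"
- "Baseline NIHSS <10"
- "Baseline ischemic core > 51 ml (based on Central Lab reading")

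Two depend on age:

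- "Age >80 with baseline ischemic core > 21ml"
- "Age < 80 and NIHSS < 20 and Baseline ischemic core >31 ml"

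Everyone else is DAWN-eligible. Both age conditions are strict inequalities. No other part of the protocol or SAP places age 80 or says whether age is in completed years or in decimals. The trial admits ages 18 to 90 (Protocol 3.3.1) and cores below 70 ml (Protocol 3.3.3), so patients at this boundary can be enrolled.

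The subgroup also appears in the July 19, 2017 memorandum bound with the SAP: "The DSMB requested that the above analysis be repeated in the subgroup of DEFUSE 3 subjects who are considered DAWN-eligible". Neither that memorandum nor the one of July 24 restates the definition.

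**The concern.** The two age lines look meant to divide patients into an older and a younger group, each with its own core limit. As written they leave out one year of age, and the default sends that year to the eligible class, subject only to the general 51 ml limit. A rule that is tighter above 80 than below it then becomes loosest at 80. Any patient caught by the gap is counted in the wrong stratum for all four outcomes in 11.1.

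The SAP writes complementary cut-points elsewhere: 12.2 splits age at under 70 against 70 and over, and ASPECTS at under 8 against 8 and over. That suggests a drafting slip. Versions 3.0 and 3.1 were issued to clarify the plan for programming before the Stanford team was unblinded, and this is the kind of point such a revision should settle. If it stays open, the programmer must either reproduce the anomaly or make an undocumented choice. A later change to a subgroup boundary would look data-driven even if it moved only one patient.

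**Working it through.** **Step 1: apply the rule literally.** Ineligible = (mRS > 1) or (NIHSS < 10) or (core > 51) or (age > 80 and core > 21) or (age < 80 and NIHSS < 20 and core > 31). The inputs are the five criteria of SAP 11.1. The plan gives no figure of its own to reproduce.

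Largest core (whole ml) still classed DAWN-eligible, with pre-stroke mRS 0-1:

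| | Age 79 | Age 80 | Age 81 |
|---|---|---|---|
| NIHSS 10-19 | 31 | 51 | 21 |
| NIHSS 20 or more | 51 | 51 | 21 |

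With NIHSS below 10 or pre-stroke mRS above 1, an 80-year-old is ineligible at every core volume. Across ages 18 to 90 at NIHSS 10-19, age 80 is the only age at which a core of 32 to 51 ml is eligible.

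**Step 2: close the gap each way** for an 80-year-old with mRS 0-1 and NIHSS of at least 10.

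- Age 80 in the older line: the largest eligible core falls from 51 to 21 ml at any such NIHSS. Cores above 21 and up to 51 ml move to ineligible.
- Age 80 in the younger line: at NIHSS 10-19 the largest eligible core falls from 51 to 31 ml, and cores above 31 and up to 51 ml move to ineligible. At NIHSS 20 or more nothing changes.

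The group that moves under both repairs is cores above 31 and up to 51 ml at NIHSS 10-19. Cores above 21 and up to 31 ml, and cores above 21 and up to 51 ml at NIHSS 20 or more, move only under the first repair.

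**Step 3: approximate numbers.** Inputs from the documents: 182 randomised (SAP 2), anticipated mean age 69 (Protocol 3.9), and DEFUSE 2 Target Mismatch core median 13 ml, IQR 5-26 (Protocol 2.1). Assumptions: age is truncated normal with SD 11 to 15; core is lognormal and resembles DEFUSE 2; age and core are independent.

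- Share aged 80: about 2.1 to 2.6%. 182 × 0.021 = 3.8 and 182 × 0.026 = 4.7, so about 4 patients.
- Log-SD of core = ln(26/5) / (2 × 0.6745) = 1.22. P(21 to 51 ml) = Φ(1.12) − Φ(0.39) = 0.22. P(31 to 51 ml) = Φ(1.12) − Φ(0.71) = 0.11.
- First repair: 4 × 0.22 = 0.9 patients (3.8 × 0.22 = 0.8 to 4.7 × 0.22 = 1.0), before the mRS and NIHSS conditions reduce it.
- Group wrong under both repairs: 4 × 0.11 = 0.4 patients before the NIHSS restriction. If 40 to 70% of patients have NIHSS 10-19 (a further assumption), the range is 3.8 × 0.11 × 0.40 = 0.2 to 4.7 × 0.11 × 0.70 = 0.4.

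**The case against.** The strongest reply is that misclassification can be judged only against the definition being copied, and the documents do not contain it. A reader might infer that every 80-year-old with a core between 21 and 51 ml is in the wrong stratum. The documents do not support that. If age 80 belongs with the younger group, cores up to 31 ml, and cores up to 51 ml at NIHSS 20 or more, are already classed correctly. This objection stands, and it limits the certain error to cores above 31 and up to 51 ml at NIHSS 10-19.

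The gap also depends on age being in whole years. With age calculated from date of birth, 80.4 counts as above 80 and only exactly 80.0 is left out. That stands too, and it is itself a reason to state the convention.

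A reader might infer that the DSMB's interim review was affected. The July 24 memorandum records that the DSMB asked for the DAWN-eligible result only after it had fixed its boundary and been sent the password for the corresponding document. The memoranda do not say which definition was used, so any link is conditional. Nor do the documents include program code, so nothing shows how age 80 was actually handled.

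Finally, the comparison is exploratory and carries no alpha or stopping boundary. That bears on the size of the point. It does not remove the gap in the text.

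**Conclusion.** The point holds as a defect in a stated rule. Given age in whole years, 11.1 leaves age 80 outside both age-specific limits, and the default produces a class at NIHSS 10-19 that agrees with neither neighbouring age for cores above 31 and up to 51 ml. That part follows from the text alone. Any error from the gap runs towards DAWN-eligible.

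The numerical effect is minor. The expected count is below one patient of 182 and the likely count is 0 or 1; for the group that is wrong under either repair, 0 is the most likely. These counts rest on the assumed age, core and NIHSS distributions, since the documents do not report how many such patients were enrolled. The consequence is limited to the exploratory DAWN-eligible against DAWN-ineligible comparison, and possibly the DSMB's subgroup analysis. It would be wrong to read this as a threat to the primary result, which uses all randomised patients as assigned and does not depend on the split.

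**What to change.** Before the study team is unblinded, revise the two age lines in SAP 11.1 so that exactly one includes age 80. The choice should follow the definition being copied, because the protocol and SAP do not show which line that is. State that age is in completed years at a named time point, such as randomisation. Record in the SAP or a memorandum whether the DSMB's DAWN-eligible analysis used the same definition.

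The cost is one character and one sentence in the SAP, and one line of code. If unblinding has already taken place, give the number of patients aged 80 whose class depends on the choice and show the comparison both ways.

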11.2. Analysis in Subgroups Defined by Sex, Race, and Ethnicity

The primary efficacy analysis will be repeated in subgroups defined by sex, race (White, African-American, Asian, Other), and ethnicity (Hispanic, Non-Hispanic). The treatment effect and corresponding 95% confidence intervals will be estimated, as described in Section 12.2.

11.3. Analysis adjusting for covariates

Please note: if the final analysis is performed with 200 patients or less, we will still perform the analysis of covariates as described below, but acknowledge that the value of this analysis may be limited because of the small sample size.

An additional ~~The secondary~~ analysis of the primary endpoint will be the same rank-based analysis comparing the distribution of the 90-day Rankin scores between treatment groups while stratifying for prognostically important covariates. The Generalized Cochran-Mantel-Haenszel test (CMH) is the analogue to the WMW, designed to test against the alternative that there is a uniform shift of size “delta” in the Rankin score distribution from one group to the other after stratification. The CMH test will be stratified by age, baseline NIHSS Score, Baseline Ischemic Core Volume (based on Central Lab reading), and Time from symptom onset to randomization (using the same categories used for the stratified randomization). A rich body of clinical research has established the prognostic importance of these covariates. Cut-points will generally follow those used in the randomization, but may be altered depending on the numbers of patients enrolled into each category.

To assess the relationship between important covariates and the size of the treatment effect, a model based regression analysis will be performed. Specifically, we will create a multivariable ordinal regression model with the 90-day Rankin outcome as the dependent variable and use a literature based model-building process. The model building process will include preliminary variable selection, a final model selection, and a final model assessment. We will evaluate each candidate predictor for proportionality and linearity (model assumptions). The correlation between candidate continuous variables will be analyzed. Variables with a rho coefficient higher than 0.7 will not be jointly entered into the final model building process - only the variable with the lowest p-value if it is less than 0.1. The base model will include treatment group. During the preliminary variable selection, potential predictors will be added to the base model one at a time to obtain a p-value for each. Variables considered candidates for the final model will have a p-value ≤ 0.1 . At the final model selection, variables will be added sequentially starting with the variable with the lowest p-value from the group of candidate predictors. The criteria for keeping a variable in the final model will be a p-value ≤ 0.05 . Each time a predictor is kept in the final model all previously added variables will be re-assessed. Any previously entered variables whose p-value has increased above 0.05 will be dropped from the model. All qualifying variables from the preliminary selection phase will be considered along with their two-way interaction with treatment assignment ~~site of arterial occlusion~~. A statistical assessment of the model will be examined by the shrinkage statistic. A shrinkage statistic below 0.85 will indicate the model is overfitting the data, and the number of predictors should be reduced. The following variables will be considered for inclusion in the adjusted model:

- Age
- Baseline NIHSS score

- Baseline ischemic core volume
- Time from symptom onset to randomization
- Sex
- Admission SBP
- Baseline glucose

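### The p > 0.05 drop rule in SAP 11.3 does not protect a main effect whose treatment interaction stays in the model, so a reported interaction can stop measuring effect modification

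*SAP*

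**What the plan says.** SAP 11.3 gives the aim of the model: "To assess the relationship between important covariates and the size of the treatment effect". The building steps are these.

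- Start: "The base model will include treatment group".
- Screening, one predictor at a time added to that base: "Variables considered candidates for the final model will have a p-value ≤ 0.1".
- Retention: "The criteria for keeping a variable in the final model will be a p-value ≤ 0.05".
- Re-assessment: "Each time a predictor is kept in the final model all previously added variables will be re-assessed".
- Backward step: "Any previously entered variables whose p-value has increased above 0.05 will be dropped from the model".
- Interactions: "All qualifying variables from the preliminary selection phase will be considered along with their two-way interaction with treatment assignment".

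No sentence says that a main effect stays while its interaction is in the model, that treatment is exempt from the backward step, or how the arms are coded. The seven candidates are age, NIHSS, core volume, time to randomization, sex, systolic pressure and glucose. Section 11 is headed as exploratory.

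**The concern.** Once a covariate-by-treatment interaction is in a model with 0/1 arm coding, the covariate's own coefficient is no longer its overall slope. It is the slope in the arm coded 0 only, estimated mainly from that arm (about 182/2 = 91 patients). Its p-value can then exceed 0.05 even though the covariate is prognostic overall. Followed literally, the backward step removes it and leaves the interaction alone.

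The remaining coefficient would still be labelled an interaction and read as effect modification, with a p-value and interval that do not belong to that question. Two programmers who coded the arms in opposite ways could report different final models from the same data. For age, NIHSS, core volume, systolic pressure and glucose taken individually, this is the only ordinal interaction model that the SAP specifies. Section 12.2 tests interactions on mRS 0–2, and section 12.4 covers only time on the ordinal scale.

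**Working it through.** The SAP gives no error rate or power for this model, so there is no plan figure to reproduce. The check is algebra followed by simulation.

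**Algebra.** Write the log-odds of a worse mRS as threshold + bT·T + bX·X + bI·T·X, with T = 0 or 1.
- Slope in arm 0: bX. Slope in arm 1: bX + bI. Effect modification is the difference, bI.
- Remove X: the arm-0 slope is forced to 0, and the coefficient on T·X now estimates approximately bX + bI.
- With slopes 0.4 (medical, coded 0) and 0.8 (endovascular), the true modification is 0.8 − 0.4 = 0.4, but the reduced model aims at about 0.8.

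**Inputs.** From the documents: n=182 randomized at the halt (SAP 2), original maximum 476, medical-arm mRS distribution (SAP Table 1), thresholds 0.05 for keeping and dropping (SAP 11.3). Assumed, because the documents give none: one standardized normal covariate, its slope in each arm (log-odds of a worse score per SD), and the treatment effect. Sequence simulated: main effect enters at p ≤ 0.05, interaction is kept at p ≤ 0.05 with the main effect present, main effect is re-tested.

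**How often the main effect is dropped, among trials where the interaction was kept** (600 trials per row):

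| Slopes medical / endovascular | n=182, medical = 0 | n=182, endovascular = 0 | n=182, arms ±1/2 | n=476, medical = 0 |
|---|---|---|---|---|
| 0.5 / 0.5 | 13/30 (43%) | 14/30 | 0/30 | 2/34 |
| 0.25 / 0.75 | 233/252 (92%) | 0/252 | 1/252 | 203/511 |
| 0.5 / 1.0 | 114/279 (41%) | 0/279 | 0/279 | 9/495 |
| 0.8 / 0.2 | 0/365 (0%) | 345/365 | 1/365 | 0/579 |
| 0 / 0.8 | 421/426 (99%) | 0/426 | 12/426 | 575/598 |

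With no true interaction (first row), the drop occurs in 13/600 = 2.2% of all trials. Two further runs gave 1.8% and 7/400 = 1.8%.

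**Slopes 0.4 / 0.8, n=182, medical coded 0** (separate runs of 400 to 2,500 trials):
- The interaction enters in 31% of trials in one run and in 134/400 = 34% in another.
- Given entry, the main effect is dropped in 73–75%, 76% and 109/134 = 81%. Over all trials that is 22% to 109/400 = 27%. With endovascular coded 0 it is 0%.
- In the dropped cases, main effect kept versus dropped: mean estimate 0.73–0.74 versus 0.93–0.94, median p about 0.01 versus 0.000005–0.0000075, 95% interval coverage 88–89% versus 15–19%.

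**Other patterns, same n and coding.** Slopes 0.3 / 0.9: drop in 79–80% of entries, coverage 94% falling to 57–59%. Slopes 0.8 / 1.2, the same true modification of 0.4: drop in 8/122 = 7% of entries in one run and 6% in another, or 1.7–2% of all trials.

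**Size of the distortion in the first three table rows, dropped cases** (n=182, medical = 0): median ratio of reduced to full estimate 1.35, 1.18 and 1.31. Median p goes from 0.017 to 0.000014, from 0.0067 to 0.000016, and from 0.0034 to 0.0000003. If the reference-arm slope is truly 0 (last row), the ratio is 1.01, so the estimate is about unbiased, although p still falls from 0.0015 to 0.000014.

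**With the main effect kept**, the interaction test rejects in 4–6% of trials when there is no interaction, and its mean over all trials is close to the true value.

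**The case against.** **The text can be read as keeping the pair together.** It considers each variable jointly with its interaction, and the interaction sentence comes after the backward step. This may be what was intended. But that sentence governs what is considered, whereas the backward step covers any variable already entered and names no exception. It is an omission, not an instruction to break hierarchy. The ambiguity stands, and so does the need to resolve it.

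**The drop is conditional and often rare.** This stands. A strong slope in the reference arm makes it uncommon, ±1/2 coding nearly abolishes it, and it is rarer at n=476 in most patterns. SAP 11.3 itself calls its stratifying covariates prognostically important, which favours the low end for those with a strong slope in the reference arm.

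**Consequence is limited.** This also stands. The analysis is exploratory, and SAP 11.3 already concedes limited value at 200 patients or fewer. The primary Wilcoxon test (9.4), the common odds ratio (9.6), the subgroup tests (12.2) and the time interaction (12.4) do not use the rule. Section 12.2 tests interaction for five of the seven candidates, though on mRS 0–2. The small-sample caveat does not, however, cover a misdefined coefficient.

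**The fix does not cure selection.** For slopes 0.4 / 0.8 the estimate already averages about 0.74 against a true 0.40 with the main effect kept, because only significant interactions are reported. The drop adds about 0.93 − 0.74 = 0.19.

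**Conclusion.** The point holds as a minor omission in an exploratory analysis. As written, the rule can remove a main effect and leave its interaction. When it does, the reported size, p-value and interval are not a valid measure of effect modification, and the result depends on an arm coding that the SAP leaves open. The percentages rest on assumed slopes and a single covariate. They show a range, not a prediction.

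Three stronger readings are not supported.

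- A reader might infer that the main effect is always removed once its interaction enters. The SAP drops it only if p exceeds 0.05, and the simulated rate runs from 0% to about 99% of entries.
- A reader might infer that ordinary prognosis will routinely be declared effect modification. If the interaction is tested with its main effect present, false entry stays near 5%. Fitting the reduced model in every trial with slopes 0.5 / 0.5 gives 72–76% significance, but the stepwise sequence does not do that.
- A reader might infer that the rule turns benefit into harm. For slopes 0.4 / 0.8 and an assumed treatment log-odds of −0.65, the true effect at +1 SD is −0.65 + 0.40 = −0.25. Among the dropped trials the model with the main effect kept already averages +0.06, and the reduced model +0.27. So 0.31 of the 0.52 shift is selection on significance and only 0.21 comes from the drop.

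**What to change.** Add to SAP 11.3: whenever a covariate-by-treatment interaction is in the model, that covariate's main effect and the treatment main effect are retained regardless of p-value. The 0.05 drop rule then applies only to terms not contained in a retained interaction.

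The cost is one sentence and a small programming rule, with no data or patients. It fits the stated purpose of SAP versions 3.0 and 3.1, which is programming clarification before unblinding. It also makes the interaction estimate independent of which arm is coded 0. It does not remove the overstatement that comes from reporting only interactions that pass p ≤ 0.05, so any interaction reported from this model should still be described as exploratory.

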11.4. Analysis under the as-treated principle

Due to the nature of the study, some subjects in the endovascular treatment plus medical management group may not receive endovascular therapy. One instance when this may occur is if symptoms resolve spontaneously between randomization and start of the endovascular procedure. Another potential reason is the absence of an arterial occlusion on the baseline angiogram (due to spontaneous recanalization). Although it would be rare, we may also see some subjects who are randomized to the medical management only group, but are treated with endovascular therapy. Therefore, after completion of the study and if there is a crossover population, we will repeat the primary analysis (the Wilcoxon-Mann-Whitney measure of superiority) ~~within the adaptive design sample~~, but with patients categorized under the as-treated principle.

